11. STATISTICS

11.1. General Overview

All subjects given ≥ 1 dose of study drug will be included in the intention-to-treat population; missing values will not be imputed but safety data (death and other AEs) will be carried forward. Subjects receiving all 3 doses and evaluable at Day 7 will constitute the per-protocol population. The expectation is that both populations will be almost identical.

Results will be summarized via summary statistics separately for each pGSN dose level in the SD and MAD portions of the trial; pooled for all placebo subjects. Additional details will be provided in a separate Statistical Analysis Plan (SAP).

11.2. Sample Size and Power Calculations

The sample size of N=6 rhu-pGSN recipients per dose level and combined placebo in the SD and MAD portions of the trial were chosen based on limiting exposure to pGSN in this initial study in the current development program. The sample sizes in this trial have the following properties in relation to interpretation of AE incidence rates (Table 7).

Table 7 presents the Minimum Sample Size such that there is 90% probability of observing at least 1 AE of a certain type if the TRUE underlying AE rate.

Table 7: Minimum Sample Size Calculations

Sample Size	TRUE underlying AE rate
6 (each pGSN dose level)	32%
8 (pooled placebo)	21%
24 (pooled pGSN)	10%

With each sample size presented in the table above, if zero AEs of a certain type are observed, one could be "90% confident" the TRUE underlying rate for that AE is at most the rate indicated above.

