7. STUDY POPULATION

7.1. Number of Subjects

A total of 32 (6 rhu-pGSN and 2 placebo recipients per dose cohort x 4 dosing levels).

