11.4. Criteria for Evaluation and Statistical Methods

11.4.1. Safety

AE data will be summarized by counts and proportions of subjects having an AE, each AE type, and an AE of each System Organ Class. These summaries will be provided for each dose and placebo (all placebo subjects combined). Serious AEs will be summarized similarly. Reasons for any early discontinuations will be summarized similarly.

Laboratory data in relation to normal range values will be summarized via counts and percentages of subjects below, within, and above the respective normal range, and by summary statistics (N, mean, median, standard deviation, minimum, maximum, 90% confidence intervals, etc.) for baseline, each observed time point, and change from baseline at each observed time point for continuous lab endpoints.

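### The sample-size table gives 21% as the 90% AE rate for 8 pooled placebo subjects; the correct figure is 25%, and 21% corresponds to only 84.8%

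*Protocol*

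**What the plan says.** Protocol Section 11.2 explains that the group sizes were chosen to limit exposure to the study drug. Table 7 then describes what those sizes can say about adverse-event (AE) rates. It gives two readings of the tabulated rate:

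- a detection probability: "there is 90% probability of observing at least 1 AE of a certain type if the TRUE underlying AE rate" is the one shown;
- a bound when no events of a type are seen: "one could be '90% confident' the TRUE underlying rate for that AE is at most the rate indicated above".

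The three rows, with the rate in per cent as the last number, are "6 (each pGSN dose level) 32", "8 (pooled placebo) 21" and "24 (pooled pGSN) 10".

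The same table appears in the Protocol Synopsis (sample size rationale) and as Table 1 in SAP Section 2.3, with the same three rates. Protocol Section 7.1 fixes the group sizes: "6 rhu-pGSN and 2 placebo recipients per dose cohort x 4 dosing levels". Protocol Section 11.4.1 says of the AE summaries: "These summaries will be provided for each dose and placebo (all placebo subjects combined").

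**The concern.** The two readings are the same equation, so the table has one formula and each row can be checked exactly. The placebo rate looks too low for its group size. Going from 6 to 8 subjects should not lower the 90% rate from 32% to 21%.

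Safety is the primary endpoint, and this table is the plan's only quantitative statement of how much the group sizes can reveal about AE rates. An understated rate errs in the unsafe direction. A reader who sees no events of a type among the eight placebo subjects is told to be 90% confident that the true rate is at most 21%, which eight subjects cannot support. The control group then appears to give a tighter bound on background event rates than it does.

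**Working it through.** **Inputs**

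- Probability of at least one event, and confidence after zero events: 90% (Protocol 11.2).
- Group sizes and stated rates: n = 6, 32%; n = 8, 21%; n = 24, 10% (Protocol Table 7, Synopsis, SAP Table 1).
- Placebo total: 2 per cohort × 4 cohorts = 8 (Protocol 7.1). The row label agrees with the design.

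**Formula.** With independent subjects and true rate p, P(at least one event) = 1 − (1 − p)^n. Setting this to 0.90 gives p = 1 − 0.1^(1/n). This is also the exact one-sided 90% upper bound after 0 events in n subjects, so both of the table's readings lead to the same number.

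**Reproducing the table**

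| n | Stated rate | 1 − 0.1^(1/n) | P(at least one event) at the stated rate |
|---|---|---|---|
| 6 | 32% | 31.87% | 1 − 0.68^6 = 90.1% |
| 8 | 21% | 25.01% | 1 − 0.79^8 = 84.8% |
| 24 | 10% | 9.15% | 1 − 0.90^24 = 92.0% |

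The n = 6 row reproduces. The n = 24 row is rounded upward, so its statement still holds. The n = 8 row does not reproduce.

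**Size of the error**

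- Rate: 25.0% − 21% = 4 percentage points, too large to be rounding.
- Chance of seeing no event at 21%: 0.79^8 = 15.2%, against the 10% implied.
- Confidence actually attached to 21%: about 85%, since 1 − 0.15^(1/8) = 21.1%.
- Subjects needed for 21%: ln(0.1)/ln(0.79) = 9.77, so 10. Check: n = 9 gives 1 − 0.79^9 = 88.0%, and n = 10 gives 1 − 0.79^10 = 90.5%.

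**Could another method give 21% for n = 8 after zero events?**

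| Method | Bound for n = 8 |
|---|---|
| Two-sided 90% Clopper-Pearson | 31.2% |
| −ln(0.1)/n approximation | 28.8% |
| Wilson, one-sided / two-sided | 17.0% / 25.3% |
| Bayes, uniform prior | 22.6% |
| Jeffreys, one-sided / two-sided | 15.1% / 20.8% |

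Only the two-sided Jeffreys bound rounds to 21%. It gives 26.4% for n = 6 and 7.6% for n = 24, against 32% and 10% stated, so it is not the table's method. Nor does it match the detection-probability definition.

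**After correction.** At p = 25%, n = 8 gives 1 − 0.75^8 = 89.99%.

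**The case against.** The arithmetic is not in dispute; the objections concern weight and detail.

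*Nothing depends on the row.* Section 11.2 says the sizes were set by exposure. Escalation follows the DSMB's review of safety through Day 7 (Protocol 6.4 and 6.5). SAP Section 11.1.2 plans counts and percentages of AEs and computes no zero-event bound. The two active-drug rows, which matter most in a dose-escalation study, are sound. All of this stands, and it keeps the point to a local correction.

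*The SAP's AE tables contain no column of eight placebo subjects.* SAP Section 3 first says that all placebo subjects form one group. It then lists placebo separately for the single-dose and multiple-dose phases, and the AE tables in Section 17 follow that split. The planned placebo columns therefore hold 2 and 2 × 3 = 6 subjects. This narrows the practical effect, because few readers would apply the n = 8 row directly to a SAP AE table. It does not make 21% correct, and Protocol 11.4.1 still commits to AE summaries with placebo pooled.

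*At exactly 25% the probability is 89.99%, a hair below 90%.* True, but the table prints whole percentages and the exact rate is 25.01%. Strict rounding up would print 26% (1 − 0.74^8 = 91.0%). No rounding rule leads to 21%.

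*The figure of 10 subjects does not show how the error arose.* Agreed. That 21% was carried over from n = 10 is only a possibility, and the finding does not rely on it.

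**Conclusion.** The pooled-placebo row is wrong in all three places where it appears, and no passage corrects it. The 90% rate for eight subjects is 25%. The stated 21% carries 84.8% probability of at least one event, which is 5.2 points short of the stated 90%. The error overstates what the control group can show.

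The conclusion assumes only independent subjects with a common event rate, which the table itself needs, and eight placebo subjects as the design specifies. The correction should be made, but its reach is small: no sample size, escalation decision or planned analysis changes, and the rows for 6 and 24 rhu-pGSN subjects are unaffected.

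**What to change.** Replace 21% with 25% in the pooled-placebo row of the Protocol Synopsis table, Protocol Table 7 and SAP Table 1. Leave 32% (n = 6) and 10% (n = 24) as they are. A footnote giving the formula 1 − 0.1^(1/n) and noting that rates are rounded to whole percentages would let a reader check every row.

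The cost is one number in three places. The stated property of the placebo group becomes slightly less favourable, and nothing else in the design or analysis changes.

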11.3. Analysis Populations

No data will be excluded from the summary statistics and analyses, and missing data will not be imputed. AEs, including death, will be carried forward. As a sensitivity analysis to the intention-to-treat population, a per-protocol population excluding subjects who missed doses and/or randomly discontinued the study before the primary Day-7 Visit will be analyzed.

11.4. Criteria for Evaluation and Statistical Methods

11.4.1. Safety

AE data will be summarized by counts and proportions of subjects having an AE, each AE type, and an AE of each System Organ Class. These summaries will be provided for each dose and placebo (all placebo subjects combined). Serious AEs will be summarized similarly. Reasons for any early discontinuations will be summarized similarly.

Laboratory data in relation to normal range values will be summarized via counts and percentages of subjects below, within, and above the respective normal range, and by summary statistics (N, mean, median, standard deviation, minimum, maximum, 90% confidence intervals, etc.) for baseline, each observed time point, and change from baseline at each observed time point for continuous lab endpoints.

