7.2. Subject Inclusion Criteria

1. Age: \geq 18 years
2. Gender: Either
3. Informed consent obtained from subject
4. Domicile: home, assisted living, rehabilitation facility, or nursing home (as long as the prospective participant is capable of providing written informed consent)
5. Duration of infection precipitating hospitalization by history <14 days
6. Planned or actual admission to hospital with a primary diagnosis of CAP within 24 hours of presentation to the hospital
7. Primary admitting diagnosis of pneumonia supported by a compatible clinical presentation with a documented infiltrate consistent with pneumonia on chest radiograph or CT, as assessed by the admitting emergency-department (ED), clinic, or ward physician or equivalent caregiver
 - Recommended (not mandatory) guidance/discretionary criteria defining patients with CAP:
 - At least 2 symptoms: difficulty breathing, cough, production of purulent sputum, chest pain
 - At least 2 vital sign abnormalities: fever, tachycardia, tachypnea
 - At least one finding of other clinical signs and laboratory abnormalities: hypoxemia, clinical evidence of pulmonary consolidation, an elevated total white blood cell (WBC) count or leukopenia
 - Chest imaging showing new (or presumed new or worsening) infiltrates
 - Receipt of antibiotic treatment prior to presentation does not exclude the patient.

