10.4. Assessment of Severity

The severity rating of an AE refers to its intensity. The severity of each AE will be categorized using the NCI CTCAE, v 4.03 (or higher). For any term that is not specifically listed in the CTCAE scale, intensity should be assigned a grade of 1 through 5 using the following CTCAE guidelines:

- Grade 1: Mild; asymptomatic or mild symptoms; clinical or diagnostic observations only; intervention not indicated
- Grade 2: Moderate; minimal, local or noninvasive intervention indicated; limiting age-appropriate instrumental activities of daily living
- Grade 3: Severe or medically significant but not immediately life-threatening; hospitalization or prolongation of hospitalization indicated; disabling; limiting self-care activities of daily living
- Grade 4: Life-threatening consequences; urgent intervention indicated
- Grade 5: Death related to AE

It is important to distinguish between serious and severe AEs. Severity is a measure of intensity whereas seriousness is defined by the criteria under [Section 10.1.2](#). An AE of severe intensity may not be considered serious.

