### **11.2.2 Biostatistical Methods**

All laboratory data collected at scheduled and unscheduled visits will be included in the listings, but only results collected as scheduled visits will be included in the summary tables.

Results for individual parameters may be reported in different units depending on the analyzing laboratory. If required, the results (and the corresponding normal range cut-off values) for individual parameters may be converted to International System of Units (S.I.) units to summarize the data.

For the all parameters where a unit value has been reported, the parameter names that will be used in the outputs will comprise of the test name and the unit of measure, for example, 'Albumin (g/L)'. Parameters will be sorted alphabetically within tables and listings.

For all parameters where a normal range limit value is reported, the normal range will be derived based on the available lower and upper limit values and any reported mathematical symbols. If both a lower and upper limit value is available, the normal range will be presented as '(Lower, Upper)'.

The reported results for each parameter with a defined normal range will be classified ('Low', 'Normal', 'High') in relation to the defined normal range limits. If a result is equal to the normal range cut-off value, the result will be considered 'Normal'.

The change from baseline values at each post-baseline visit will be calculated for all parameters with continuous results (except for specific gravity and pH).

The decimal precision for each parameter will be based on the maximum number of decimals to which the reported result or the normal range limits are presented to in the raw data. The results and normal ranges will be displayed to the same decimal precision in the listings.

If a result for a parameter that is normally considered continuous is reported as a range (i.e., the result for basophils is reported as '<0.01' for a single time point), the result may be converted to a numeric value that is smaller than the reported result to contribute to the derivations and the summary statistics. Any conversion rules that are applied will be highlighted in the footnotes of the affected tables and listings. The original reported result value will however be included in the listing.

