The laboratory result tables will present summary statistics for each laboratory parameter within the specific test panel. For each parameter, summaries will be presented for the baseline and each scheduled post-baseline visit. In addition, summaries will be presented for the change from baseline values at each scheduled post-baseline visit.

Additionally, counts (%) of number subjects with values out of normal range at each scheduled time point will also be presented along with shift tables that will represent the changes in normal range categories across post-baseline time points.

The listings of laboratory parameters will include all the information (fields) collected. In addition, the observations that are used as the baseline record (value) for each parameter will be flagged, and the change from baseline values at each post-baseline visit will be presented.

For all parameters, standardized values will be reported.

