**Programming Note:**  
 Include all CBC Parameters and all scheduled time points.

Clinical cut-off date: DDMMYYYY  
 Program: filepath\_name, Output: filepath\_name (version x.x) Created: DDMMYYYY HH:MM

Table 14.3.4.1.1.2 MAD: Summary of CBC (Summary of Actual and Change from Baseline Values) by Timepoint  
Protocol: BTI-201  
Safety Population

Clinical cut-off date: DDMMYYYY  
Program: filepath\_name, Output: filepath\_name (version x.x) Created: DDMMYYYY HH:MM

Programming Note:  
Repeat Table 14.3.4.1.1.1  
Include all CBC Parameters and all scheduled time points.  
  
Include: rhu-pGSN 6 mg/kg;  
          rhu-pGSN 12 mg/kg;  
          rhu-pGSN 24 mg/kg;  
          Combined Active;  
          Combined Placebo;  
          Overall

Table 14.3.4.1.2.1 SD: Summary of CBC Shifts from Baseline (Low, Normal, High)  
 Protocol: BTI-201  
 Safety Population

		Baseline 					
Parameter	Result Classification	Low n (%)	Normal n (%)	High n (%)	Missing n (%)	Total n (%)	
Hemoglobin (g/L)	Day 2						
	Low	xx (xx.x%)	xx (xx.x%)	xx (xx.x%)	xx (xx.x%)	xx (xx.x%)	
	Normal	xx (xx.x%)	xx (xx.x%)	xx (xx.x%)	xx (xx.x%)	xx (xx.x%)	
	High	xx (xx.x%)	xx (xx.x%)	xx (xx.x%)	xx (xx.x%)	xx (xx.x%)	
	Missing	xx (xx.x%)	xx (xx.x%)	xx (xx.x%)	xx (xx.x%)	xx (xx.x%)	
	Total	xx (xx.x%)	xx (xx.x%)	xx (xx.x%)	xx (xx.x%)	xx (xx.x%)	
	Day 3 or 4						
	Low	xx (xx.x%)	xx (xx.x%)	xx (xx.x%)	xx (xx.x%)	xx (xx.x%)	
	Normal	xx (xx.x%)	xx (xx.x%)	xx (xx.x%)	xx (xx.x%)	xx (xx.x%)	
	High	xx (xx.x%)	xx (xx.x%)	xx (xx.x%)	xx (xx.x%)	xx (xx.x%)	
	Missing	xx (xx.x%)	xx (xx.x%)	xx (xx.x%)	xx (xx.x%)	xx (xx.x%)	
Total	xx (xx.x%)	xx (xx.x%)	xx (xx.x%)	xx (xx.x%)	xx (xx.x%)		

rhu-pGSN: 6 mg/kg  
(N=xx)

etc. etc.

Note Baseline is defined as the last valid, non-missing assessment prior to first study drug administration. Unscheduled visits not included in post baseline assessments.

Programming Note:  
 Also Include: Placebo, Overall  
 Include all CBC Parameters and all scheduled time points.

Clinical cut-off date: DDDMMYYYY  
 Program: filepath\_name, Output: filepath\_name (version x.x) Created: DDDMMYYYY HH:MM

Table 14.3.4.1.2.2 MAD: Summary of CBC Shifts from Baseline (Low, Normal, High)  
Protocol: BTI-201  
Safety Population

Clinical cut-off date: DDMMYYYY  
Program: filepath\_name, Output: filepath\_name (version x.x) Created: DDMMYYYY HH:MM

Programming Note:  
Repeat Table 14.3.4.1.2.1  
Include all CBC Parameters and all scheduled time points.  
  

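### The laboratory shift tables cross only Low, Normal and High at scheduled visits, so no table counts by dose group the subjects who worsen from an already abnormal baseline

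*Protocol*

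**What the plan says.** Protocol 11.4.1 states that laboratory data "will be summarized via counts and percentages of subjects below, within, and above the respective normal range". The same sentence goes on to plan summary statistics, including minimum, maximum and 90% confidence intervals, for baseline, for each time point and for "change from baseline at each observed time point for continuous lab endpoints".

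SAP 11.2.2 applies the categories as follows. Each result with a normal range is "classified ('Low', 'Normal', 'High') in relation to the defined normal range limits". The SAP then plans counts of out-of-range values at each scheduled time point, and "shift tables that will represent the changes in normal range categories across post-baseline time points". The mock shells for Tables 14.3.4.1.2.x (CBC), 14.3.4.2.2.x (coagulation) and 14.3.4.3.2.x (metabolic profile) cross the baseline class with the class at each visit, plus Missing and Total. Nothing is graded within Low or within High.

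The same SAP section also says that "summaries will be presented for the change from baseline values at each scheduled post-baseline visit". Unscheduled results go to the listings only, and SAP Section 3 keeps repeat assessments out of summary tables and figures.

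Three other provisions bear on the point:
- **Listings.** The 16.2.8.x shells show, per subject, the value, change from baseline, reference range, High/Low flag and clinical significance.
- **Adverse events.** Protocol 9.2.6 and 10.6 turn some laboratory abnormalities into AEs. Protocol 10.4 grades AEs by CTCAE v4.03 or higher, and SAP 11.1.2 tabulates them by grade.
- **Primary endpoint.** Protocol 5.2.1 includes clinically significant laboratory abnormalities through Day 7.

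**The concern.** A shift table is meant to show, by arm, how many subjects got worse. A three-class table can do so only for subjects who start inside the range or on the opposite side of it. A subject who is High at baseline stays in the High-to-High cell however far the value rises, and the same applies to falls within Low. Conversely, a trivial step across a limit counts as a shift.

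The trial enrols acutely ill inpatients, so some abnormal baselines are to be expected. The discretionary guidance in Protocol 7.2 lists "an elevated total white blood cell (WBC) count or leukopenia" among the findings that support the diagnosis. Raised urea scores in CURB-65, and CRP and BUN are in the panel. At stake is how readily a dose-related move from mildly to markedly abnormal can be read from the by-arm tables, on a component of the primary safety endpoint.

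**Working it through.** The plan states no figure on this point, so there is none to reproduce. The check sets the planned outputs side by side and then runs a small illustration.

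**1. What each planned output shows when a subject is High at baseline and higher later**

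| Output | Shows the worsening? | Counts such subjects by arm? |
|---|---|---|
| Out-of-range counts (SAP 11.2.2) | No: High at both times | No |
| Shift tables 14.3.4.1.2.x to 14.3.4.3.2.x | No: High-to-High cell | No |
| Change-from-baseline tables 14.3.4.1.1.x to 14.3.4.3.1.x | Yes, in mean, SD or maximum, at scheduled visits | No |
| Listings 16.2.8.x | Yes, subject by subject | No |
| AEs by CTCAE grade (SAP 11.1.2) | Only if reported as an AE | Only those reported |

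A peak on an unscheduled or repeat draw reaches the listings, and the AE tables if it is reported, but none of the first three rows. No laboratory table uses a worst post-baseline value.

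**2. How many subjects can show an upward shift**

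Input: 6 active subjects per dose level (Protocol 11.2). Let *b* be the share above range at baseline for a given test. The documents give no value of *b*, so the full range is shown. Subjects able to shift upward = 6 × (1 − *b*).

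| *b* (assumed) | 6 × (1 − *b*) | Worsening subjects left unshifted if all six worsen, 6 × *b* |
|---|---|---|
| 0% | 6 | 0 |
| 25% | 4.5 | 1.5 |
| 50% | 3 | 3 |
| 75% | 1.5 | 4.5 |
| 100% | 0 | 6 |

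**3. Shift count against change from baseline, on invented data**

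Upper limit 40; six baseline values of 80, 90, 100, 70, 60 and 85, all High.

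- *All six values double.* Each change equals its baseline value. Shifts: 0 of 6. Mean change = 485/6 = +80.8, median +82.5, minimum +60, maximum +100. The continuous table shows this plainly.
- *One value rises from 80 to 400, the others stay put.* Shifts: 0 of 6. Changes are 320 and five zeros: mean 320/6 = +53.3, median 0, SD 130.6, maximum +320. The continuous table shows it through the mean, SD and maximum, but not the median.

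**4. The clinical-significance flag**

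Vital signs and EKG have by-arm tables of Normal, Abnormal NCS and Abnormal CS (SAP 11.3.2 and 11.4.2; Tables 14.3.4.5.x and 14.3.4.7.x). For laboratory data the CS/NCS flag appears only in the listings.

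**The case against.** A reader might infer that laboratory safety rests only on Low/Normal/High, so that worsening in an already abnormal subject would look like no change. The documents do not support that. The sentence in Protocol 11.4.1 that sets the three classes also plans change-from-baseline statistics with minimum and maximum, and SAP 11.2.2 repeats the change-from-baseline summaries for every panel. In step 3 both invented scenarios show up in those summaries. With 6 active subjects per dose level, the listings can be read subject by subject. Laboratory results that are clinically significant or need treatment become AEs, and these are graded and tabulated by grade. All of this stands.

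A reader might also infer that most subjects enter out of range. Protocol 7.2 calls its criteria recommended, not mandatory. White count is one option among several, and it can be low as well as high. No CURB-65 threshold is an entry criterion. The extent of baseline abnormality is therefore unknown here.

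These answers do not supply the missing count. The continuous tables go visit by visit and do not link change to baseline status. The AE route depends on treatment, a DLT or the investigator's judgement rather than a numeric trigger, and Protocol 10.6 folds laboratory abnormalities into a clinical syndrome where possible. Further worsening in a sick patient may be put down to the pneumonia and never be reported as an AE.

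**Conclusion.** The concern holds in a limited form, as a minor reporting gap. The by-arm categorical laboratory tables cannot register worsening within High or within Low, and they leave out peaks seen only on unscheduled or repeat draws. No planned table counts, by dose group, the subjects who worsen from an abnormal baseline. That much follows from the text and shells without any assumption.

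How much it matters depends on how many subjects enter out of range for a given test. The documents do not say, so the figures of 6 down to 0 able to shift upward span an assumed range and are not an estimate. They describe movement in one type of table, not lost detection: the values and changes are still collected, summarised and listed.

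**What to change.** Keep the Low/Normal/High tables. In SAP 11.2.2 and the table list, add for each panel and dose group a shift from baseline grade to worst post-baseline grade:

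- Treat low and high directions separately.
- Take the worst valid post-baseline result, including unscheduled and repeat results. This needs a stated exception to the scheduled-visits rule in SAP 11.2.2 and the repeat-assessment rule in SAP Section 3.
- Use CTCAE v4.03 where it grades the parameter. Where it does not, use prespecified multiples of the normal limit or of baseline. The protocol gives only the generic grade descriptions, so check each test before finalising the list, in particular CRP, urea and raised white count. If these are ungraded and simply left on Low/Normal/High, the gap stays open for them.
- Report the number of subjects rising by at least 1 grade and by at least 2 grades.

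The results and normal limits are already planned for collection, so the cost is extra programming, a lookup to specify and larger tables.
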